As already mentioned, the goal of this study is to investigate the "low LV mass phenotype" in patients with RA and its contributors in an attempt to elucidate the pathophysiology pathways that may connect RA with alterations in the myocardium and the evolution to heart failure. 3D-Echo will be used to measure the LV mass. Cardiac PET-CT imaging will be used to evaluate myocardial function (cardiac output, ejection fraction), microvasculature function (myocardial perfusion) and myocardial inflammation (F18-FDG uptake).

The research questions to be addressed with the study visit I are the following:

- i) Are anti-CCP antibodies or other RA-specific characteristics (e.g., disease duration, activity, severity) associated with lower LV mass (or other LV parameters of structure/function)?
- ii) What is the prevalence, the degree and correlates of microvascular dysfunction in RA? Is it associated with low LV mass or reduced global or regional contractility? Is it associated with systemic, articular and/or myocardial inflammation?
- iii) What are the prevalence, patterns, distribution and severity of inflammation as measured by F18-FDG uptake in myocardial PET imaging? Are intensity and/or distribution of F18-FDG uptake correlated with low LV mass or global or regional contractility? Does the severity/distribution of F18-FDG uptake correlate with levels of systemic and/or articular inflammation?

For the second aim of this study the goal is to evaluate the effect of TNF inhibitors on the myocardium. For the 50 patients undergoing randomization and the controls the questions to be addressed will be the following:

- i) Are global measures of LV structure (e.g., mass) or contractility (e.g., ejection fraction) affected (reduced or increased) by treatment with TNF antagonists? Is there a different effect compared to alternative therapy?
- ii) If microvascular dysfunction and/or inflammation are present before treatment, do they improve with treatment with TNF compared to alternative treatment? If parameters improve only with TNF inhibitor, this would suggest that TNF inhibitors exert a local anti-inflammatory effect on the myocardium mechanistically different compared to alternative treatment.
- iii) If treatment-induced improvements in microvascular dysfunction and/or inflammation (F18-FDG uptake) are

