Linear mixed effects (MIXED) regression models will be used to assess trends in LV structure and functional outcomes over time between the two visits for the patients who will undergo randomization reevaluation with PET-CT and 3D Echocardiogram, while controlling for potential confounders. The data will include PET-CT studies for 25 RA patients receiving TNF antagonists and 25 RA patients receiving alternative treatment, and PET-CT studies for 15 non-RA patients. The data are longitudinal since LV outcomes are measured for each person at 2 different time points. Since repeated measures tend to be correlated within a person, mixed models with both fixed and random effects will be used to adjust for this correlation. We will use unstructured correlation structure given that each visit will occur roughly around a fixed time since study visit I, and use robust standard error estimates to conduct statistical inferences. To study the TNF inhibitor effects on LV structure or functional outcomes, visit-specific indicators, RA status, TNF treatment status, and visit x TNF treatment interaction will form the bases for the mean model. The visit-specific indicators will capture the time trend of LV outcomes over the study period, the RA status will delineate the overall mean difference in LV outcomes between RA and non-RA, with the TNF treatment status indicator and its interaction with visit indicators capturing the baseline difference in LV outcomes between TNF treated and non-treated groups and the potential TNF treatment effect on LV outcome over time, respectively. Actual TNF inhibitor dosage could be used in place of TNF status indicator in the model if necessary, and other potential covariates could be added into the model for confounding adjustment. For example, inflammation markers could be added into the model to examine whether any TNF treatment effect is mediated through the change in systemic inflammation. Similar modeling approaches can be used to study all research questions of interest using the corresponding outcomes and their hypothesized predictors listed in those questions to be addressed. For any binary outcomes in this type of regression analysis, e.g. indicator of whether a LV outcome exceeding certain critical value, generalized linear mixed effects models (GLIMMIX) can be used to study the odds of such outcome as a function of the independent variables.

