We will obtain valuable information on LV structure/function outcomes for the cross-sectional visit, as well as for change in these outcomes over 6 months, for 3 groups of study participants, 25 RA patients treated with TNF-antagonist, 25 RA patients treated with triple treatment or alternative, and 15 non-RA participants with otherwise similar characteristics. For continuous outcomes we will obtain mean, standard deviations, and skewness (to inform us whether certain variables may need transformation before analyses so that sample size/power evaluation for future studies may need to be based on transformed data) for cross-sectional as well as the change over time measurements, and the correlations between two consecutive measurements over time. For binary variables we will obtain prevalence estimates and odds ratios as estimates of association between two repeated binary measures over time. Even accounting for a possible 15% drop out rate of participants, the correlation estimate will have precision ranged approximately between within +/- 0.33 for a correlation of 0.50 and within +/- 0.09 for a correlation of 0.90. For prevalence of binary outcomes, our estimate will be ranged approximately from within +/- 17.9% for a prevalence of 50% to +/-10.7% for a prevalence of 90%. To estimate the power of detecting a 24 week (6 month) change in an LV myocardial outcome within the TNF treated RA group, with a 2-sided alpha of 0.05 and N=22 (accounting for possible drop out), we calculated the minimal detectable change based on cross-sectional SDs and various values for within person correlation between outcome measures at subsequent visits based on data from previous studies performed by the same investigator group. For example with a conservative SD of 1.8 L/min for cardiac output (CO) and 4.2 mL/m^2 for stroke volume (SV) and the correlation between subsequent visits being 0.2 we will have 80% power to detect a 24 week (6 month) change of 1.47 l/min for CO or 3.42 ml/m^2 for SV or more in the TNF inhibitor treated RA group. Similarly in order to estimate power for comparing changes between the TNF inhibitor treated group, the triple therapy treated group and the normal control group we based our calculations with comparing the changes between those groups with one way ANOVA assuming a 15% drop out and a 2-sided alpha of 0.05. We will have 80% power to detect any set of 3 group differences/changes if the SD of the changes is 0.444 or greater. We will have 80% power to detect a difference through the 3 group-one-way-ANOVA if the mean 24 week (6 month) change in SV for the TNF inhibitor group is 5.2ml/m^2 or higher while the mean change for the other two groups is 0. To provide a context regarding the number used above as an expected change in SV we would like to mention here that in our pilot data we observed a change in SV of 12.5mL/m^2 or higher with TNF inhibitor treatment in patients with RA.

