
Based on preliminary data RA patients had an LV mass of 120± 27 grams while normal people had an LV mass of 147

$\pm 40$  gram. For a change in left ventricle mass from 120 to 147 grams over the 6 month period we will have an 80% power to detect this improvement of LV mass in 25 patients treated with TNF inhibitor with a one sided alpha of 0.05 assuming a correlation of 0.35. We will have more than 85% power to detect a difference of 27 grams of mass between the TNF inhibitor treated group and the triple therapy treated group.

For changes in FDG uptake indicative of myocardial inflammation we assume that according to AHA guidelines a significant change in the intensity of FDG uptake would be equal to a decrease of 50%. We will have more than 80% power to detect such a difference between the TNF inhibitor treated group and the triple therapy treated group after 6 months of treatment with a 2 sided alpha of 0.05.

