#### PET for inflammation:

F18 fluorodeoxyglucose (FDG) is a glucose analog that is taken up in metabolically active cells including myocytes and tumor cells. It is also taken up in regions of inflammation. Uptake into myocytes depends on substrate, insulin

levels and GLUT4 transporter. Uptake by tumor and by regions of inflammation presumably uses GLUT1, a non insulin dependent transporter. Positron emission tomography will be performed on all patients from the base of the skull to the chest cavity after injection of F18 FDG and CT scan for neck and chest will be performed. Images will be obtained one to two to three hours after injection. Glucose levels will be checked at the time of injection using a standard clinical protocol. Uptake of tracer will be reported as global or focal and scored. Intensity of uptake will be scored according to a scale from 0 to 3. Level 0 will be no myocardial uptake. Level 1 will be myocardial uptake less than the mediastinal uptake. Level 2 will be uptake in the myocardium equal to mediastinal uptake. Level 3 will be uptake in the myocardium that is greater than mediastinal uptake. Extent of uptake will be assessed as number of specific regions of increased intensity.

A computerized program will also be utilized to assess for the standardized uptake value (SUV) which will give a continuous variable based on quantitative uptake.

CT scan images of the neck and/or chest will be fused with PET scan images to correlate the regions with regions of increased uptake.

PET-CT for the evaluation of ventricular function:

PET assessment of ventricular function is performed during gated myocardial perfusion imaging. With gated PET, accurate measurements are made of LV end-diastolic and end-systolic volumes as well as of LV ejection fraction. Additionally this method allows for assessing regional and global ventricular function both at rest and stress.

Reliability of Cardiac PET Image Reading:

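### The claim of more than 80% power for a 50% fall in FDG uptake is unsupported: it names no measure, SD, baseline, control-arm change or n, and makes no allowance for patients without uptake at baseline

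*Combined protocol and SAP*

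**What the plan says.** Section 2b (Sample size and power calculations) assumes, with reference to AHA guidelines, that "a significant change in the intensity of FDG uptake would be equal to a decrease of 50" per cent. It continues: "We will have more than 80% power to detect such a difference between the TNF inhibitor treated group and the triple therapy treated group". The comparison is set at the six-month visit, two-sided at the 5% level. These two sentences are the whole FDG calculation.

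The measure is described in Section 3 under PET for inflammation. There, "Intensity of uptake will be scored according to a scale from 0 to 3", where 0 is no myocardial uptake and levels 1 to 3 rank the myocardium below, equal to or above the mediastinum. The same section adds a computed standardized uptake value (SUV), a continuous measure. On timing it says: "Images will be obtained one to two to three hours after injection".

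Aim 2 question ii in Section 2a is conditional: "If microvascular dysfunction and/or inflammation are present before treatment, do they improve with treatment with TNF compared to alternative treatment". The prevalence of FDG uptake is itself listed there as a question for Visit I. The criteria for the randomised part (Section 6) select on CDAI above 10 and do not mention FDG uptake. The planned data are "25 RA patients receiving TNF antagonists and 25 RA patients receiving alternative treatment".

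**The concern.** Other outcomes in Section 2b come with inputs. Cardiac output and stroke volume have SDs (1.8 L/min and 4.2 mL/m²), a correlation of 0.2 and N=22. LV mass has means, SDs and a correlation of 0.35. FDG has only a percentage and a power, so the claim cannot be checked.

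Two features of the design make the gap matter. First, two FDG measures are collected and neither is designated as the outcome for the arm comparison, so the choice can be made after the data are seen. Second, patients without uptake at baseline cannot show a fall. If they are analysed they dilute the contrast; if they are left out the arms shrink. The plan does not say which will happen or how many such patients it expects.

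FDG uptake is the study's direct measure of myocardial inflammation. If its power is unknown, a null result on that question cannot be interpreted.

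**Working it through.** **Inputs from the documents.** Difference: 50% of baseline. Two-sided alpha: 0.05. Planned n: 25 per arm. Dropout: 15% ("Even accounting for a possible 15% drop out rate of participants"), which gives 0.85 × 25 = 21.25; the plan itself uses 22 for the TNF arm. The documents do not say whether dropout was applied to the FDG figure.

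**Not in the documents.** For FDG there is no SD, baseline mean, correlation between visits, control-arm change, test or prevalence of uptake. Every value of these below is an assumption.

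**1. The plan's own figure.** It cannot be reproduced. The most that can be done is to solve for the condition under which it would be true.

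**2. Condition for 80% power, unadjusted change scores.** Treat 50% of the baseline mean as the between-arm difference and assume every patient has uptake. If d is the standardised difference that a two-sample t-test detects with 80% power, the largest admissible SD of change is 0.5/d of the baseline mean.

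| n per arm | d | Largest SD of change, % of baseline mean |
|---|---|---|
| 25 | 0.809 | 61.8 |
| 22 | 0.865 | 57.8 |
| 21 | 0.886 | 56.4 |

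At 22 per arm, power by assumed SD of change is:

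| SD, % of baseline mean | 40 | 50 | 60 | 70 | 80 | 100 |
|---|---|---|---|---|---|---|
| Power | 98% | 90% | 77% | 64% | 53% | 37% |

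The claim is true or false according to an SD that the plan does not give.

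**3. Effect of baseline adjustment.** With equal SD σ at both visits and correlation ρ, the variance of change is 2σ²(1−ρ), and the residual variance after adjusting for baseline is σ²(1−ρ²). Their ratio is (1+ρ)/2, so the admissible SD of change becomes 57.8%/√((1+ρ)/2) at 22 per arm:

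- ρ = 0.5: 57.8/0.866 = about 67%
- ρ = 0.2: 57.8/0.775 = about 75%

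The mixed model in Section 2a fits a free baseline difference between treatment groups plus a visit-by-treatment term. With two visits, this amounts to comparing changes, so it does not obtain this gain.

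**4. Dilution by patients without uptake.** Let a share p have uptake. Those patients have an SD of change of 50% of their baseline mean, with a mean fall of 50% on TNF inhibitor and none on triple therapy. The others do not change. The difference in mean change is 0.5p. The variance of change is p(0.25+0.25) − 0.25p² on TNF inhibitor and 0.25p on triple therapy.

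For p = 0.5 the variances are 0.1875 and 0.125, with average 0.156 and SD 0.395, so d = 0.25/0.395 = 0.63. Simulating the t-test on change with 22 per arm (20,000 runs) gives:

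| Share with uptake | 100% | 75% | 50% | 30% |
|---|---|---|---|---|
| Power | 90% | 76% | 54% | 32% |

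**5. Restricting to patients with uptake instead.** At 50% prevalence, 11 of 22 per arm remain and the SD limit falls to 40% of the baseline mean; at an SD of 50%, power is 61%. At about 30%, 7 per arm remain and the limit is 31%; at an SD of 50%, power is 41%.

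**6. What the 0-3 score can show.** From level 0 no fall is possible. From 1 the only fall is 100%. From 2 it is 50% or 100%. From 3 it is 33%, 67% or 100%. A fall of exactly 50% exists only from level 2; a fall of at least 50% is possible from levels 1, 2 and 3.

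**The case against.** A reader might infer that the 50% fall is defined on the 0-3 score, which could not show it for most values. The documents do not support this. Section 2b speaks only of intensity of uptake. Section 3 does attach that word to the score, but also provides SUV, on which a 50% fall is well defined. The guideline credited with the criterion is not available here to settle the scale. Even on the score, the difficulty is confined to a fall of exactly 50% in one patient: three of the four levels allow a fall of at least 50%, and a group mean can be halved. What stands is ambiguity about the measure.

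A reader might also infer that the plan assumes no fall on triple therapy. It does not say so. The control-arm change is missing, and 50% may be meant as the between-arm difference itself. Nor does the FDG sentence state its n; that it refers to the whole arms is the natural reading of its wording.

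The sponsor can also say that SUV is already collected, that Section 2a extends similar models to all research questions, and that the power may well exceed 80%. All three are correct. They limit the finding to an unsupported statement and an analysis that can be improved cheaply.

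Finally, the timing sentence is garbled and could describe serial images. Nothing shows that the two visits would differ in uptake time, but nothing in that section requires them to match.

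**Conclusion.** The claim of more than 80% power is unsupported, not refuted. It holds if all 22 patients per arm have uptake and the SD of change is below about 58% of the baseline mean (unadjusted), or below about 67% to 75% with baseline adjustment at correlations of 0.5 to 0.2. It fails at larger SDs. It can also fail at moderate ones if many patients lack uptake: at an SD of 50%, unadjusted, power drops from 90% to 54% at half prevalence and 32% at 30%.

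These figures rest on assumed SDs, correlations and prevalences, on equal SDs at the two visits for the adjusted limits, and on a between-arm difference of 50% of baseline among patients with uptake. The documents give no FDG values to replace these assumptions. The practical gain lies in fixing the measure, the analysis and the scan timing before the data are read; rewording the power sentence alone would add little.

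**What to change.** 1. In Sections 2a and 2b, name SUV as the FDG outcome for the arm comparison, analysed as Visit II SUV adjusted for baseline SUV in all randomised patients. Keep the 0-3 score as descriptive. Report patients with baseline uptake as a pre-specified subgroup, which answers aim 2 question ii directly.

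2. In Section 3, replace the one-to-three-hour wording with a requirement that each patient is imaged at the same post-injection time at both visits.

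3. In Section 2b, replace the power claim with a conditional one that matches the analysis. For example: with 22 per arm, all with uptake, and a between-arm difference of 50% of baseline, an unadjusted comparison of changes has 80% power only if the SD of change is at most about 58% of the baseline mean. Baseline adjustment relaxes this to about 67% to 75% for visit correlations of 0.5 to 0.2, assuming equal visit SDs. Power falls as fewer patients have uptake (assumed SD 50%, unadjusted: 90%, 54% and 32% at 100%, 50% and 30% prevalence). Label the SDs, correlations and prevalences as assumptions and state the assumed control-arm change.

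The cost is wording, a less favourable power statement and tighter scan scheduling. SUV is already computed, so no procedure is added.

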### 3. STUDY PROCEDURES (See Appendices I,II and III)

Study procedures that are done outside the context of usual care for patients with RA are the following:

i.

Cardiac PET-CT imaging will be used to evaluate myocardial perfusion, myocardial inflammation and myocardial function.

(this section includes references)

[figure not shown]
#### PET Perfusion Imaging:

The demonstration and quantification of myocardial hypoperfusion/ischemia with nuclear imaging techniques is a well-established method to predict cardiovascular disease progression risk in cardiac patient populations (1). Myocardial hypoperfusion is a powerful predictor of cardiac endpoints such as nonfatal myocardial infarction and death. Myocardial blood flow determined by quantitative PET is an independent predictor of the coronary circulatory dysfunction in cardiac clinical events and shows superiority to conventional methods. In a recent review, Schindler et al report that functional alterations in cardiac circulation measured by PET imaging appear to be prognostically superior to structural assessments of coronary vessel disease (i.e. coronary angiography, calcification) in predicting future cardiac events. PET measurement of coronary flow reserve provides a sensitive index for evaluating changes in coronary disease severity. A review of a series of seven studies involving more than 1000 patients indicates that perfusion imaging with PET is a sensitive and specific method to diagnose severity of coronary disease (1). These studies found an average sensitivity and specificity of approximately 90% (1,2).

PET measurement of myocardial perfusion is an ideal measure of coronary and microvascular involvement for the purposes of this study, and is preferable to other available techniques. In addition to prognostic significance, there are several reasons for the choice of quantitative PET for myocardial perfusion. The use of PET addresses common limitations of other methods such as coronary angiography. That is, percent diameter stenosis of coronary vessels obtained by means of coronary angiography is poorly related to flow capacity or coronary flow reserve of the coronary arteries. Gould and colleagues have reported that progression or regression of coronary vessels stenosis may involve complex changes in which the integrated hemodynamic effects, absolute arterial lumen area, and length are not accounted for by any single geometric measurement such as percent stenosis. Furthermore, quantifying single focal stenoses on coronary arteriograms does not account for multiple stenoses, diffuse anatomic lesions, or disorders of arterial vasomotion. Therefore, coronary angiography, including quantitative coronary angiography, does not reflect the perfusion capacity of the integrated coronary artery circulation that is diseased in atherosclerosis. It has thus been suggested that the measurement of size and severity of myocardial perfusion abnormalities by PET-CT better reflects changes in the integrated flow capacity of the coronary circulation that are more relevant to long-term clinical outcomes and more sensitive to modest changes in lifestyle modification interventions than other diagnostic methods (1,2). PET-CT imaging also provides accurate information about microvascular blood flow and endothelial dysfunction.

#### PET Imaging Protocol:

PET utilizes radiolabeled agents (such as  $[^{13}\text{N}]$  ammonia) for the measurement of myocardial blood flow at rest and during pharmacological stress using agents such as the vasodilator adenosine. The percent increase in blood flow from

rest to stress provides a measure of coronary blood flow reserve, including microvascular flow. Normal subjects without cardiovascular disease or risk factors have a coronary flow reserve on the order of 4. They are capable of a 4 fold increase in blood flow with pharmacological stress, while patients with coronary artery disease demonstrate attenuations in coronary flow reserve.

We will perform PET myocardial perfusion imaging using [N] ammonia for the measurement of myocardial blood flow at rest and during pharmacological stress using the vasodilator adenosine. PET imaging will be performed in a blinded procedure in all subjects under the supervision of [name], Investigator and Director of the Columbia University Medical Center Cardiac Positron Emission Tomography Center. [name] will otherwise have no contact with the study subjects and will not be aware of participants' clinical info collected during the study. The PET data will be acquired on the Siemens Biograph Truepoint 40 PET/CT scanner. The camera has 4mm resolution and scan time performance superior to the prior generation of PET imaging devices. The Siemens biograph uses computed tomography (CT) acquisition for attenuation correction as well as co-registration with the emission image. PET data are collected in 47 planes 3.375 mm thick that cover a range of 16 cm. A dose of 10 mCi of [N] ammonia is injected and a 10 min dynamic acquisition is started. The process is repeated, including a second attenuation scan, for the stress study. The injections of ammonia are separated by at least 40 minutes to allow the first injection to decay to a level where it will not interfere with the second study. All scanning is performed in 2D gated mode and reconstructed with filtered back projection using a Hann filter cutoff at 1 cycle/cm.

